**Table 8-2 Assessment Schedule, Relapse Retreatment**

Period	Retreatment for relapse																				
Visit Name	Pre-retreatment	Day 1 (1st infusion)							Day 2	Day 8	Day 15 (2nd infusion)						Day 22	Day 29 (3rd infusion)			
Days	-14 to -1	1							2	8	15						22	29			
Time (post-dose)	-	-2h ±1	-1h	0h	20 min & 40min	2h	4h	24h	-	-2h ±1	-1h	0h	40min	2h	4h	-	-2h ±1	-1h	0h	40min	
Mini International Neuropsychiatric Interview (MINI)	S 																				
Physical Examination	S																				
Short Physical Examination		S								S							S				
Electrocardiogram (ECG) 			X		X		X	X			X		X		X			X		X	
Pulse rate 			X		X	X	X	X	X		X		X	X	X	X		X		X	
Blood Pressure 			X		X	X	X	X	X		X		X	X	X	X		X		X	
Respiratory Rate			S		S	S	S	S	S		S		S	S	S	S		S		S	
Body Temperature	X										X							X			
Body Weight	X										X							X			
Pregnancy and assessments of fertility	X 	S 								S 							S 				
Hematology		X						X	X	X						X	X				
Urinalysis		X						X	X	X						X	X				
Clinical Chemistry	X 	X 						X	X	X						X	X				
Alcohol Test and Drug Screen 		S							S	S						S	S				
Memory Assessment Questions					S 								S 							S 	
Oxygen saturation		S 									S 							S 			

Period	Retreatment for relapse																			
Visit Name	Pre-retreatment	Day 1 (1st infusion)						Day 2	Day 8	Day 15 (2nd infusion)						Day 22	Day 29 (3rd infusion)			
Days	-14 to -1	1						2	8	15						22	29			
Time (post-dose)	-	-2h ±1	-1h	0h	20 min & 40min	2h	4h	24h	-	-2h ±1	-1h	0h	40min	2h	4h	-	-2h ±1	-1h	0h	40min
Study drug administration				X 								X 							X 	
Concomitant medications	X																			
Adverse Events	X 																			

Period	Retreatment for relapse			
Visit Name	Day 29 (3rd infusion)		Day 36	End of Retreatment
Days	29		36	43
Time (post-dose)	2h		4h	-
Mini International Neuropsychiatric Interview (MINI)				
Physical Examination				
Short Physical Examination				S
Electrocardiogram (ECG) 			X	X
Pulse rate 	X		X	X
Blood Pressure 	X		X	X
Respiratory Rate	S		S	S
Body Temperature				X
Body Weight				X

Period	Retreatment for relapse			
Visit Name	Day 29 (3rd infusion)		Day 36	End of Retreatment
Days	29		36	43
Time (post-dose)	2h	4h	-	-
Pregnancy and assessments of fertility				S 
Hematology			X	X
Urinalysis			X	X
Clinical Chemistry			X	X 
Alcohol Test and Drug Screen 			S	S
Memory Assessment Questions				
Oxygen saturation	S 			
PK blood collection		X		
Montgomery-Asberg Depression Rating Scale (MADRS)		X	X	X
Study drug administration				
Concomitant medications	X			
Adverse Events	X 			

Period	Retreatment for relapse			
Visit Name	Day 29 (3rd infusion)	Day 36	End of Retreatment	
Days	29	36	43	
Time (post-dose)	2h	4h	-	-

X Assessment to be recorded in the clinical database or received electronically from a vendor
 
S Assessment to be recorded in the source documentation only
 
 Start at 40 min timepoint, subsequently, if memory gaps/ amnesia is present, it must be assessed at least once per hour until resolution
 
 Only M.I.N.I. for MDD
 
 Triplicate
 
 Serum, (FSH test to be performed locally for fertility assessment, see Section 8.4.4)
 
 Urine
 
 In addition for this visit TSH test
 
 Results to be obtained before collection of any clinical and patient questionnaires
 
 Every 15 minutes from pre-dose to 4 hours from the start of dose administration
 
 Administered at approximately the same time each dosing day, in the morning or early afternoon at latest.
 
 In case of AE of cystitis or other lower urinary tract event, the PRO Bladder Pain/ Interstitial Cystitis symptom score (BPIC-SS) should be completed
 
 In case sample is not taken in fasting stage, a repeat chemistry sample must be done on day 1, in fasting condition
 
 Assessment to be completed at the 40 minute timepoint only
				

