## Clinical Safety

MIJ821 has been tested in a limited number of participants – in a FIH study (Phase 1 Study CMIJ821X2101) in healthy volunteers and a Phase 2a clinical study (CMIJ821X2201) in patients with TRD. Although it has been shown to be safe and well tolerated at the dosages to be used in this Phase 2b study, there may be unknown risks associated to MIJ821.

In the FIH study (CMIJ821X2101), dissociative and cognitive adverse events were dose-related, occurring at 0.24 mg/kg or higher doses, but not at 0.16 mg/kg or lower doses. Frequency of amnesia in particular was somewhat higher at 0.32 mg/kg than other doses. With repeated dosing, dissociative and cognitive adverse events were seen only in two participants in the 0.32 mg/kg group. Dissociative and cognitive adverse events were mild, had time to onset after infusion of 0.78-4.43 hours, and resolved in 0.67-5.4 hours. Amnesia had a longer time to onset (range of onset 0.83-7.93 hours) and lasted longer (range to resolution 0.02-23.85 hours). Other adverse events were not common, nor severe.

In the PoC Study CMIJ821X2201 conducted in 70 treatment-resistant depression patients for 6 weeks, the clinical picture with longer observation on treatment was consistent with FIH data. The study also included one Ketamine treatment arm as a positive control.

Most AEs were mild in severity and were reported in 39 subjects (55.7%). Moderate and severe AEs were reported in 13 (18.6%) and 10 (14.3%) subjects, respectively and one life-threatening AE of suicide threat was also reported in one subject (MIJ821 0.32 mg/kg biweekly treatment group). SAEs occurred in 5 subjects: in the MIJ821 0.16 mg/kg biweekly treatment group, 1 subject had an asthma exacerbation; in the MIJ821 0.32 mg/kg biweekly treatment group: 3 subjects experienced 4 SAEs: one subject with atrial fibrillation, one subject with worsening of major depression, and in one subject two SAEs: suicide threat (Day 29) and suicide attempt (Day 70). In the placebo treatment group one subject had a suicide attempt. All SAEs were assessed as not study drug related by the investigator.

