Analysis of AEs of interest showed that dissociative side effects, sedation and amnesia (investigator reported) were seen at both the 0.16 mg/kg and 0.32 mg/kg MIJ821 doses. Amnesia in particular was dose dependent and more common at the higher MIJ821 dose (42.1% with MIJ821 0.32 mg/kg vs 9.5% with MIJ821 0.16 mg/kg pooled doses). No AEs of amnesia was seen in Ketamine or Placebo arms. About one-quarter of patients in each active treatment group experienced dissociative side effects (23.8% for 0.16 mg/kg pooled dose and 26.3% in 0.32 pooled mg/kg dose), versus 50% with Ketamine and 10% with placebo. Sedation was seen at both active doses (14.3% at the lower pooled dose and 21.1% at 0.32 mg/kg pooled dose vs 10% with ketamine and 0% with placebo).

Time to onset of dissociative side effects, amnesia and sedation was short, occurring within the 40 minutes of infusion in most cases for both MIJ821 doses and for placebo, though somewhat longer than with ketamine. Median time to onset for adverse event of sedation was shorter for the lower MIJ821 dose (pooled 0.16 mg/kg dose, 0.25 hours) than the higher dose (pooled 0.32 mg/kg dose, 1.46 hours), versus 0.10 hours for ketamine and no cases (0.0 hours) for placebo.

Most events of amnesia resolved within 4 hours (median time to resolution was 3.27 hours). Median time to resolution for dissociation ranged from 5.25 hours for MIJ821 0.16 mg/kg

pooled dose versus 3.72 hours for MIJ821 0.32 mg/kg pooled dose, and shorter times for ketamine (1.02 hours) and placebo (2 hours). Events of sedation resolved faster for the pooled 0.16 mg/kg dose than 0.32 mg/kg pooled dose (median time 1.6 hours vs 2.5 hours). Ketamine time to resolution was 0.47 hours.

At both MIJ821 investigated doses, increases in mean supine systolic and diastolic blood pressure were observed at the first sampling time of 1 hour after start of the 40 min infusion. The placebo-adjusted mean change from baseline in supine SBP and DBP appeared to peak between 2 to 4 hours after start of infusion ( $< 20$  mmHg) with a clear trend of recovery to baseline within 4 hours (DBP) and 6 hours (SBP) after start of infusion.

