Alcohol Test and Drug Screen 				S	S	S	S	S	S
Memory Assessment Questions	S 								
Oxygen saturation	S 								

[illegible]

Period	Core Period				Extension			End of Study	
Visit Name	Day 29 (3rd infusion)			Day 36	End of Core	2 weeks F/U 	4 weeks F/U 	Every 4 weeks 	End of Study
Days	29			36	43	57	71	99	-
Time (post-dose)	40min	2h	4h	-	-	-	-	-	-
Study drug administration									
Concomitant medications	X								
Study completion information									X

X Assessment to be recorded in the clinical database or received electronically from a vendor
 
S Assessment to be recorded in the source documentation only
 
 Subsequently, if memory gaps/ amnesia is present, it must be assessed at least once per hour until resolution
 
 Baseline assessments
 
 Equip participant with Holter monitoring device to be able to start the recording at -1 H predose.
 
 Triplicate
 
 Serum, (FSH test to be performed locally for fertility assessment, see Section 8.4.4)
 
 Urine
 
 If a result has not been obtained by a central lab, local lab result will be used to determine patient eligibility.
 
 In addition for this visit TSH test
 
 In case sample is not taken in fasting stage, a repeat chemistry sample must be done on day 1, in fasting condition.
 
 Results to be obtained before collection of any clinical and patient questionnaires
 
 Every 15 minutes from pre-dose to 4 hours from the start of dose administration
 

 
 The interval between two learning sessions should be in the range of 60 to 90 minutes
 
 No meals should be allowed from 4 h pre-dose to 1hr after infusion start on Day 1
 
 Administered at approximately the same time each dosing day, in the morning or early afternoon at latest.
 
 In case of AE of cystitis or other lower urinary tract event, the PRO Bladder Pain/ Interstitial Cystitis symptom score (BPIC-SS) should be completed
 
 Mandatory visits including for non-responders at End of Core
 
 For non-responders, this visit should be replaced by End of study visit
									

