2.6.1.1 Adverse events of special interest / grouping of AEs

Based on the current available information, following events are considered Adverse Events of Special Interest (AESI). This information is subject to change, based on the availability of incremental clinical experience with MIJ821. MedDRA search criteria for AESIs will be identified by the latest version of electronic Compound Case Retrieval Strategy (CRS).

- Dissociation
- Sedation
- Cardiovascular effects (BP changes and QT interval prolongation on ECG)
- Respiratory effects (difficulty in breathing, changes in oxygen saturation)
- Suicidality (suicidal ideation or behavior)
- Memory gaps/ amnesia
- Cystitis or other lower urinary tract adverse events

AESI will be summarized by risk name and PT respectively for Core Period and Retreatment Period. The time to onset on each dosing day, starting from first dosing, starting from the most recent dosing and time to resolution (starting from first onset date) of each AESI at risk level will be summarized by descriptive statistics. For multiple AESIs per subject, the earliest onset time and the latest resolution time will be counted per subject. For AESI occurred on dosing day, a listing will be provided with the time to onset (starting from first dosing, starting from the most recent dosing) and time to resolution (starting from onset date) by risk name and PT term for each participant. AESIs occurred on non-dosing days will be presented by listing in similar manner.

In addition, the by AESI category as listed above and by PT summary will be provided for AESI identified by investigator and reported in CRF AE form under the Adverse Event Category of "Adverse event of special interest". A listing will be provided as well.

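### In the legible schedule, a participant negative on the memory questions at 40 minutes is not asked them again, although amnesia began later than that in the first-in-human study

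*Protocol*

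**What the plan says.** **Schedule.** In Protocol Table 8-2 (relapse retreatment) the memory assessment row is marked in the 40-minute column on Days 1, 15 and 29. Footnote 1 reads "Start at 40 min timepoint, subsequently, if memory gaps/ amnesia is present, it must be assessed at least once per hour until resolution". On Day 1, where 20 and 40 minutes share a column, footnote 12 adds "Assessment to be completed at the 40 minute timepoint only". In Table 8-1 (Core and Extension) footnote 1 gives the repeat rule without a start time: "Subsequently, if memory gaps/ amnesia is present, it must be assessed at least once per hour until resolution". In both tables the answers are recorded in source documents only.

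**Earlier onset data (Protocol Section 4.5, Clinical Safety).** For the first-in-human study: "Amnesia had a longer time to onset (range of onset 0.83-7.93 hours) and lasted longer". The same paragraph describes that study's dissociative and cognitive events as "occurring at 0.24 mg/kg or higher doses, but not at 0.16 mg/kg or lower doses". For the proof-of-concept study in patients: "Time to onset of dissociative side effects, amnesia and sedation was short, occurring within the 40 minutes of infusion in most cases".

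**Analysis.** Memory gaps/amnesia is a listed adverse event of special interest (AESI). AESIs belong to the secondary safety endpoint for the Core Period (Protocol Table 2-1). SAP 2.6.1.1 summarises, for each AESI, "The time to onset on each dosing day, starting from first dosing, starting from the most recent dosing". SAP 2.6.4.6 states that individual memory assessment results will be presented.

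**The concern.** The repeat rule is conditional on a positive finding. Once a participant answers correctly at 40 minutes, nothing in the legible schedule brings the questions back, even though staff return at 2 h and 4 h for blood pressure, pulse and respiratory rate. One of the protocol's two sources of onset data places amnesia entirely after that single check.

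Two outputs are exposed. Incidence of this AESI may be too low if late cases are noticed less reliably than early ones, because a participant may not be aware of a memory gap and may not volunteer it. The onset summary in SAP 2.6.1.1 may also be pulled towards 40 minutes, the only time at which everyone is asked. Amnesia showed a clear dose gradient in the proof-of-concept study (9.5% at 0.16 mg/kg and 42.1% at 0.32 mg/kg, pooled regimens), so its ascertainment bears on the choice of dose.

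**Working it through.** The plan states no figure to reproduce. The check compares times.

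**Inputs.** Scheduled check at 40 min (Table 8-2). First-in-human amnesia onset 0.83 to 7.93 h (Protocol Section 4.5). Observation for 4 h from the start of each infusion (Protocol Section 3.2). Infusion length 40 min. The documents do not say whether onset was timed from the start or the end of infusion, so both readings are shown.

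**Step 1: the check on the same scale.** 40/60 = 0.67 h.

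**Step 2: earliest and latest first-in-human onset.**

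| Onset timed from | Earliest, after start | Gap after the check | Latest, after start | Beyond the 4 h observation |
|---|---|---|---|---|
| Start of infusion | 0.83 × 60 = 49.8 min | 49.8 − 40 = 9.8 min | 7.93 h | 7.93 − 4 = 3.93 h |
| End of infusion | 49.8 + 40 = 89.8 min | 89.8 − 40 = 49.8 min | 7.93 + 0.67 = 8.60 h | 8.60 − 4 = 4.60 h |

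On either reading, every reported first-in-human onset follows the scheduled check, and the range runs past the observation period.

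**Step 3: proof-of-concept data.** The statement that most onsets fell within the infusion pools dissociation, amnesia and sedation, and gives no separate onset for amnesia. The same paragraph puts median sedation onset at 1.46 h for 0.32 mg/kg, so at least half of those sedation onsets were later than 0.67 h. The pooled statement therefore does not hold for every event and dose. Median time to resolution of amnesia was 3.27 h, so an event that began during the infusion would usually still be present at 40 min. The single check suits early events and is blind to later ones.

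**Step 4: could a merged cell hide 2 h and 4 h checks?** In Table 8-2 the Day 29 columns for 2 h and 4 h are printed as a separate block. Oxygen saturation is marked there and the memory row is blank, so the 40-minute reading is firm. In Table 8-1 the Core Day 1 and Day 15 rows are illegible. The Day 29 memory mark sits in the first column, but so does the mark for oxygen saturation, which is measured every 15 minutes up to 4 h. Position alone therefore does not prove one check only, and the Core reading is an inference.

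**The case against.** **The scheduled questions are not the only safeguard.** A reader might infer that the search for amnesia stops at 40 minutes. It does not. Protocol Section 3.2 names amnesia among the events to be monitored on site during the 4-hour observation and requires at least 24 hours in hospital after the Day 1 infusion. Section 10.2.5 has trained investigators seek the diagnosis by clinical evaluation, including memory questions and time to onset. This stands, and it limits the point to structured, timed assessment: Section 10.2.5 fixes no times.

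**The first-in-human data are the less applicable source.** That paragraph places dissociative and cognitive events above this trial's highest dose, and the proof-of-concept data come from patients who included those on 0.16 mg/kg. This also stands in part. But amnesia was reported in 9.5% of patients at 0.16 mg/kg, so the absence of such events at that dose in the first-in-human study did not carry over to patients, and a statement about most cases leaves later ones.

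**No under-count is demonstrated.** A reader might multiply the 9.5% by an assumed late fraction to estimate missed cases. The documents give no such fraction, and SAP 2.6.1.1 counts AESIs from coded and investigator-reported adverse events, not from these source-only questions. For the same reason, onset times need not pile up at 40 minutes by construction, since onset can be established clinically. Clustering is a risk, not a necessity.

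**Parts of the plan are not visible.** Section 10.2.4 and other safety-scale text are removed, and Table 8-1 footnote 13 refers to learning sessions of an assessment not shown. Further scheduled cognitive checks cannot be excluded.

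**Conclusion.** The point holds as a gap in structured ascertainment. It is firm for retreatment (Table 8-2) and inferred for the Core Period (Table 8-1). A participant negative at 40 minutes has no further scheduled memory question in the legible schedule, while all first-in-human onsets came 9.8 min or more after that check and the proof-of-concept text covers only most events, pooled over three kinds. Detection of later amnesia rests on the 4-hour observation and untimed clinical evaluation. Late cases may be under-ascertained and recorded onset times may cluster near 40 minutes; the size of either effect cannot be derived from the documents.

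The conclusion assumes that no removed text schedules an equivalent memory check. It does not touch the primary efficacy analysis. The protocol should also explain how its two sets of onset data support a single check at 40 minutes.

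**What to change.** 1. In Tables 8-1 and 8-2, repeat the same memory questions at the existing 2 h and 4 h post-dose assessments of every infusion, whatever the 40-minute result. Keep the hourly follow-up rule for positives.
2. Record the answers in the clinical database. They are now source-only, which sits badly with the presentation promised in SAP 2.6.4.6. That section can then show them by assessment time. Where a clinical onset time is recorded, SAP 2.6.1.1 should go on using it.
3. In Protocol Section 4.5 or the schedule rationale, reconcile the first-in-human and proof-of-concept onset data with the assessment times.

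The cost is a few minutes per infusion from staff already present, one added data-capture item, and wording changes in both documents. One limit remains: onsets after 4 h would still depend on adverse event reporting.

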## 8.1 Screening

Screening will be performed while the participant is hospitalized. The duration of the Screening Period is up to 48 hours. In case a safety laboratory assessment at screening is outside of the range specified in the exclusion criteria, the assessment should be repeated prior to randomization on Day 1. If the repeat value remains outside of the ranges specified in the exclusion criteria, the participant must be screen failed.

Investigators may re-screen a participant only once if the investigator is reasonably certain that reasons for screen failure will be resolved prior to or during a repeat screening attempt. Reasons to re-screen may include but are not limited to the following:

- Laboratory value(s) out of range due to sampling error or that might be within range after medically-appropriate supplementation
- The participant has a medical condition that can be stabilized or resolved prior to the repeat screening attempt
- Additional time is required following the participant's last dose of an excluded medication (see [Table 6-2](#))

A participant must provide a new informed consent prior to the initiation of any re-screening procedures (e.g. participant must be reconsented). A new subject number will be assigned.

### 8.1.1 Information to be collected on screening failures

Participants who sign an informed consent form and are subsequently found to be ineligible prior to randomization will be considered as screen failures. The reason for screen failure should be recorded on the appropriate CRF. The demographic information, informed consent, and Inclusion/Exclusion pages must also be completed for screen failure participants. No other data will be entered into the clinical database for participants who are screen failures, unless the participant experienced a serious adverse event during the screening phase (see [Section 10.1.3](#) for reporting details). If the participant fails to be randomized, the IRT must be notified within 2 days of the screen fail that the participant was not randomized.

Participants who are randomized and fail to start treatment, e.g. participants randomized in error, will be considered an early terminator. The reason for early termination should be recorded on the appropriate CRF.

## 8.2 Participant demographics/other baseline characteristics

Participant demographic and baseline characteristic data to be collected on all patients include age, sex, ethnicity. Country-specific regulations should be considered for the collection of demographic and baseline characteristics in the CRF.

Background information that should be reported includes history of previous treatments, relevant medical history, or current medical conditions, diagnosis of disease.

Investigators will have the discretion to record abnormal test findings on the medical history CRF whenever in their judgment, the test abnormality occurred prior to the informed consent signature.

## 8.2.1 Mini International Neuropsychiatric Interview (M.I.N.I.), Version 7.0.2

The Mini International Neuropsychiatric Interview (M.I.N.I.) is a brief structured clinical interview for major psychiatric disorders in DSM-5 and ICD-10. It is divided into diagnostic modules including screening questions corresponding to the criteria for each disorder that allow the physician to assess whether the diagnostic criteria have been met.

The full M.I.N.I. version will be provided to the sites. M.I.N.I. will be administered on paper by qualified personnel at screening and at relapse (Table 8-1, Table 8-2)

Module A (Major Depressive Episode), Module B (Suicidality), Module C (Manic and Hypomanic Episodes), Module K (Psychotic Disorders and Mood Disorders with Psychotic Features), Module I (Alcohol Use Disorder), Module J (Substance Use Disorder, Non-Alcohol), Module Y (Borderline Personality Disorder) and Module Z (Suicidality Disorders Classification Interview) should be used for eligibility purposes as defined in the eligibility criteria (Section 5). Other modules should be used, as needed. The results of the interview must be added to the source records to confirm the eligibility criteria.

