### SoC can be adjusted or modified after the relapse retreatment, as clinically warranted. Extension Follow-up Duration

[figure not shown]
All participants must complete a follow-up period after the End of Core Period visit (Day 43):

- For participants who are neither remitters nor responders at the End of Core Period (Day 43) [Section 3.2](#), the follow up will last 8 weeks and consists of 3 mandatory visits (the 2 weeks Follow-up visit, the 4 weeks Follow up visit and the End of Study visit occurring 8 weeks after Day 43)
- For participants who are responders or remitters at the End of the Core Period (Day 43), and who do not experience any relapse, the Extension Period will last 52 weeks. This will consist of the 2 weeks Follow-up visit, the 4 weeks Follow-up visit, and thereafter Follow-up visits occurring every 4 weeks up to End of Study visit at Week 52
- Participants who are responders or remitters at the End of the Core Period (Day 43), and who relapse during the Extension Period, will receive one course of retreatment with MIJ821.
  - After that course of retreatment:
    - The participant will resume the 4 weekly Follow-up visit schedule (E.g., if the 6 weeks relapse retreatment period occurred from week 19 to 25, the participant will not perform visits week 20 and week 24, and will resume the follow-up at week 28).

- The duration of the follow up will be as per the initial schedule up to Week 52 or clinical worsening, whichever comes first, but they must complete at least 8 weeks follow-up period (see [Section 6.1.4](#)). Signs of clinical worsening may include worsening of depressive mood, need for SoC adjustments, a suicidal attempt, hospitalization for depression or suicidal ideation or behavior. For patient management see [Section 3.4](#), subsection Relapse and Clinical Worsening.
- Participants who are responders or remitters at the End of the Core Period (Day 43), and who relapse during the Extension Period but do not meet the weight requirements of 50-120kg (inclusive), cannot be retreated for the relapse and must be discontinued. The Extension period for these participants should last at least 8 weeks before the discontinuation.

The total duration of the Extension Period is 52 weeks, maximum. Therefore, the last date of confirmed relapse enabling access to the retreatment period is 38 weeks. If a participant relapses on or after that date, the participant must complete the End of Study visit as soon as possible.

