## Criteria for retreatment in case of relapse in the extension period

Meeting any of the following criteria will be considered a relapse and will be followed by a retreatment:

- MADRS total score  $\geq 22$  for 2 consecutive visits separated by 5-14 days AND meeting DSM-5 criteria for MDE (confirmed with M.I.N.I. Module A (Major Depressive Episode) to be eligible for relapse retreatment. The date of the first MADRS assessment will be the date of relapse. In addition, those participants who are responders at the End of Core period ( $\geq 50\%$  improvement) but are not remitters (MADRS  $\leq 12$ ), should demonstrate  $\geq 50\%$  worsening from their MADRS total score reported at the End of Core Period (End of Core Visit).

OR

- Hospitalization for worsening depression or any other clinically relevant event suggestive of a relapse (i.e. suicide attempt, or hospitalization for suicide prevention) AND meet DSM-5 criteria for MDE (independently of the MADRS score; confirmed by M.I.N.I. Module A (Major Depressive Episode). The start date of hospitalization will be the start date of relapse. In case of a clinically relevant event, without hospitalization, the start date of the event will be used as the relapse date.

Because assessments for relapse need to occur at two consecutive visits separated by 5-14 days, scheduled visits and/or unscheduled visits can be organized. Relapse confirmation can be performed either at the Pre-retreatment visit or before the first infusion given for retreatment. If several relapse criteria are met, the first will be defined as the date of relapse.

In case of clinical worsening after participant already received one course of retreatment for relapse, the patient must be discontinued, as soon as 8 week follow up from the last dose of MIJ821 was administered. These patients will be managed according to investigator judgement with SoC that can be adjusted or modified after the relapse retreatment, as clinically warranted.

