2.5.1 Secondary endpoints

To assess the effect of MIJ821 on sustained response and remission, following secondary efficacy endpoints will be evaluated:

- Proportion of participants meeting response criteria ($\geq 50\%$ reduction from baseline in MADRS total score) over time in the Core Period.
 - Participants who do not meet the criterion or discontinue Core Period prior to the time point due to any reason or with missing score (baseline and/or post baseline) will not be considered as "a responder" at that timepoint.
- Proportion of participants meeting criteria for sustained response ($\geq 50\%$ reduction from baseline in MADRS total score sustained for a period of at least four weeks) in the Core Period

- The sustained response ideally requires all scheduled assessments over four weeks achieving 50% reduction from baseline. However, if there is one or more missing assessment(s) between two responses, the response will be assumed to be sustained over missing assessment(s), unless other specified. For example, one participant observed a response at Day 1 4 hours, Day 29 -2 hours, however missed the assessment at 24 hours, Day 8, Day 15 and Day 22, this participant is still considered as meeting the sustained response. The missing due to study discontinuation will not be imputed. Participants who do not meet the criterion will not be considered as “a responder” at the timepoint.
- Proportion of participants meeting remission criteria (MADRS total score of ≤ 12) over time in Core Period
 - Participants who do not meet the criterion or discontinue prior to the time point due to any reason or with missing score (either at baseline or post baseline) will not be considered as “a remitter” at that timepoint.
- Proportion of participants meeting criteria for sustained remission (MADRS total score of ≤ 12 sustained for a period of at least four weeks) in the Core Period
 - The rule for sustained remission is the similar with sustained response. Participants who do not meet the criterion will not be considered as “a remitter” at the timepoint.
- Proportion of participants meeting criteria for relapse over fixed period in the Extension Period
 - The definition and criteria of relapse could be referred to protocol section 3.4. The relapse will be evaluated by investigator and reported in the CRF form “Relapse and re-treatment criteria”. Participants without relapse reported will not be counted.

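### Relapses from week 38 of the Extension have no scheduled visit with the M.I.N.I. that confirms them, so the 12-month relapse rate may be under-reported

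*Protocol*

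**What the plan says.** Protocol 3.4 defines relapse by two routes. The first is a MADRS total of at least 22 at two visits 5-14 days apart, "AND meeting DSM-5 criteria for MDE (confirmed with M.I.N.I. Module A (Major Depressive Episode) to be eligible for relapse retreatment". The second is hospitalization or another relevant clinical event, again with a major depressive episode, "independently of the MADRS score; confirmed by M.I.N.I. Module A (Major Depressive Episode".

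On timing, protocol 8.2.1 states: "M.I.N.I. will be administered on paper by qualified personnel at screening and at relapse (Table 8-1, Table 8-2". It refers the reader to Tables 8-1 and 8-2. Table 8-1 marks the M.I.N.I. at Screening only; the Extension and End of Study cells are blank. Table 8-2 marks it at the Pre-retreatment visit only, as a source-document item with the footnote "Only M.I.N.I. for MDD". Section 3.4 adds: "Relapse confirmation can be performed either at the Pre-retreatment visit or before the first infusion given for retreatment".

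Section 3.3 sets week 38 as the last date on which a confirmed relapse gives access to retreatment, and continues: "If a participant relapses on or after that date, the participant must complete the End of Study visit as soon as possible".

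SAP 2.5.1 takes relapse from the investigator's entry on the relapse and retreatment criteria form, with the rule "Participants without relapse reported will not be counted". SAP 2.5.2 reports the proportion relapsed at 1, 2, 3, 6, 9 and 12 months among responders and remitters in the Extension Set, and a Kaplan-Meier analysis of time to first relapse.

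**The concern.** The definition of relapse depends on an interview that the schedule provides only on the way to retreatment. From week 38 that path is closed. The participant is directed to a visit with no M.I.N.I., and a prompt final visit may come before a second MADRS score can be obtained. No passage tells the site to confirm a relapse that cannot lead to retreatment, so practice may differ between sites.

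The 12-month Extension exists to describe durability of effect and relapse. A late relapse that is never confirmed and reported is treated as no relapse in the 12-month proportion, and adds no event to the Kaplan-Meier curve. The visible SAP text gives no censoring rule. If such a participant is censored at an early End of Study visit, the censoring is informative, because follow-up ended on account of deterioration. A confirmation that was not collected cannot be recovered at analysis.

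**Working it through.** **The plan's own figure.** The 38-week cut-off follows from durations in protocol 3.3 and 6.1.4: 52 weeks of Extension - 6 weeks of retreatment - 8 weeks of minimum follow-up = 38 weeks. It reproduces exactly.

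**Exposed window.** Weeks 38 to 52 are 14 of 52 weeks, or 26.9% of Extension time.

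**Can scheduled visits confirm a MADRS relapse?** By then follow-up is four-weekly (3.3), with a window of 3 days either way (Section 8). Two consecutive scheduled visits are at least 28 - 3 - 3 = 22 days apart, more than the 14 days allowed. The second MADRS therefore needs an extra visit, which before week 38 the Pre-retreatment visit can supply.

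**Worst-case size.** The documents give no relapse rate, so the rates here are assumptions. Let p be the true 12-month proportion, and suppose that no relapse from week 38 on is recorded. With a constant hazard the recorded proportion is the proportion relapsed by week 38:

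recorded = 1 - (1 - p)^(38/52)

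| True p | Recorded | Points lost | Share of relapses lost | Recorded if half are captured |
|---|---|---|---|---|
| 10% | 7.4% | 2.6 | 26% | 8.7% |
| 30% | 22.9% | 7.1 | 24% | 26.5% |
| 50% | 39.7% | 10.3 | 21% | 44.9% |
| 70% | 58.5% | 11.5 | 16% | 64.3% |

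The Kaplan-Meier curve would show the same: with no event recorded after week 38, it stays flat from there.

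**Falling hazard.** With a Weibull curve of shape k, recorded = 1 - (1 - p)^((38/52)^k), still with no late capture:

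- k = 0.7: 30% reads 24.9% and 50% reads 42.7% (17% and 15% of relapses lost).
- k = 0.5: 30% reads 26.3% and 50% reads 44.7% (12% and 11% lost).

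**Full capture.** If every late relapse is confirmed at an unscheduled visit and reported, the loss is zero.

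**Other time points.** Six months is week 26, before the window. Nine months is about week 39 (52 x 9/12), so only its last week is exposed.

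**Arm contrast, worst case.** A true 50% against 30% is a difference of 20 points and a ratio of 1.67. Recorded, it is 39.7 - 22.9 = 16.8 points and a ratio of 39.7/22.9 = 1.73.

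**The case against.** The strongest reply is that the protocol already lets sites confirm these relapses. Section 3.4 requires a deteriorating participant to be assessed and accepts unscheduled visits for the purpose. Section 8 allows unscheduled visits with their own case report forms. Section 8.2.1 asks for the M.I.N.I. at relapse without limiting it to participants who will be retreated, and the sentence in 3.4 on where confirmation happens is permissive. Section 3.3 speaks of a participant who relapses, so End of Study can be read as following the confirmation and not replacing it. The SAP analyses relapse in the Extension Set and does not require that retreatment was given.

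All of this stands, and it defeats one stronger reading: that late relapsers cannot be confirmed, so the 12-month rate must miss them. What remains is that the only places 3.4 names for confirmation are on the retreatment path, that the tables 8.2.1 points to have no slot for a relapse without retreatment, and that prompt exit sits badly with a 5-14 day wait.

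A reader might also infer that participants barred by weight or pregnancy are missed in the same way. In general they are not: Table 8-2 places body weight, the serum pregnancy test and the M.I.N.I. at the same Pre-retreatment visit. The gap would reach them only if the bar were already known, for example from a weight at an Extension visit, and that visit were skipped.

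A third inference, that arm differences must shrink, holds only on the absolute scale. In the worked example the ratio rises slightly.

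Finally, SAP 2.5.2 tests no hypothesis on secondary efficacy endpoints, and the 24-hour primary analysis is untouched. Both are true and limit the consequence to the description of durability.

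**Conclusion.** The concern holds as a gap in the schedule with a risk of under-reporting. Relapses on or after week 38 have no scheduled visit with the M.I.N.I. that both relapse routes require, and the End of Study instruction in 3.3 is not reconciled with the 5-14 day confirmation in 3.4. Relapses before week 38 are provided for.

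The effect on the 12-month proportion lies between zero, with full capture, and about 3 to 11 points, with no capture, a constant hazard and a true rate of 10% to 70%. A falling hazard gives a smaller loss, 11-17% of relapses in the cases worked. The rates and the hazard shapes are assumptions, and the share of late relapses that sites would capture is unknown. Proportions through 6 months are unaffected and the 9-month one barely so.

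**What to change.** Three changes, none of which alters a retreatment or clinical management rule:

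1. In Table 8-1, mark M.I.N.I. Module A as conditional on suspected relapse at Extension follow-up, unscheduled and End of Study visits, so that the tables match 8.2.1.
2. In protocol 3.4 and SAP 2.5.1, state that relapse is confirmed and reported on the relapse form whether or not retreatment follows.
3. Reconcile the prompt End of Study visit in 3.3 with the 5-14 day second MADRS in 3.4, so that sites know how a relapse from week 38 is confirmed before follow-up ends.

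The cost is a table row, a few sentences, and one short interview module, already in use in the trial, for a few participants. Some late relapsers would also need the second MADRS visit that 3.4 already requires.
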